## Protocol Abstract for 2019 Continuing Review of PTSD-mTBI Study 03/26/2019

- Instructions: Include a 1-5 page (do not exceed 5 pages) abstract containing the following content (as applicable). Please attach a separate PDF document.

### **Purpose**

The overall aim of this proposal is to investigate the potential short and long term effectiveness of a cognitive training program that targets executive control functions in veterans with co-morbid posttraumatic stress disorder (PTSD), history of mild traumatic brain injury (mTBI), and cognitive difficulties. Both PTSD and TBI have been associated with cognitive dysfunction which may lead to functional impairment and poor community reintegration. PTSD can be highly debilitating not only due to emotional dysregulation, but also due to deficits in the cognitive control processes

### **Research questions and Hypotheses**

Question 1: What are short and long term effects of GOALS training on neuro-cognitive performance in Veterans with co-morbid PTSD and Mild TBI?

- *Hypothesis 1:* Participants in GOALS training will demonstrate greater improvements on untrained standardized neuropsychological measures of complex attention and executive function compared to participants in EDU training.
- *Hypothesis 2:* At the six month follow-up, participants will on average demonstrate improvements on standardized neuropsychological measures of complex attention and executive function relative to their baseline performance, suggesting persistence of GOALS training benefits.

Question 2: What are short and long term effects of GOALS training in veterans with co-morbid PTSD and Mild TBI on complex real-life functional task performance and daily functioning ?

- *Hypothesis 1:* Participants who participate in GOALS training will demonstrate greater improvements on an untrained complex real-life functional task than participants who participate in control EDU training.
- *Hypothesis 2:* Participants who participate in GOALS training will report greater improvements on self report measures of functional performance in their daily lives compared to participants who participate in control EDU training.
- *Hypothesis 3:* Training benefits will persist six months post GOALS training, as measured by participants' improvements in complex functional task performance and on self-report measures of everyday functional performance, relative to their pre-GOALS performance

Question 3: What are short and long term effects of GOALS training in veterans with co-morbid PTSD and Mild TBI on self-report measures of emotional regulation?

*Hypothesis 1*: Participants who participate in GOALS cognitive training will report greater improvements on self report measures of emotional regulation compared to participants who participate in control EDU training.

*Hypothesis 2*: At six month follow-up, participants will demonstrate improvements on self report measures of emotional regulation relative to their pre-GOALS performance, suggesting persistence of training benefits.

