### ***Interventions***

Participants who meet the inclusion criteria will be enrolled in the study and randomized to either five week Brain Health Education (EDU) or Goal-Oriented Attentional Self-regulation (GOALS) training. After 5 weeks, those who enter with EDU will receive 5 weeks of GOALS, while those who begin with GOALS will have no further formal training. Both groups will participate in assessments at baseline, week 5 and week 10. Long-term follow-up will be conducted at 6 months.

The GOALS training involves ten 2 hour sessions of group-based training, three individual 1 hour training sessions, and approximately 20 hours of home practice. It is conducted in a small group format with 2-5 participants, and 2 therapists per group.

The GOALS intervention emphasizes two key components: First, regulation of distractibility (redirection of attention to goal-relevant processes and the filtering of non-relevant 'noise', especially in the context of distractions) is addressed with attention regulation training. Training emphasizes principles of applied mindfulness-based attention regulation to redirect cognitive processes towards goal-relevant activities even when distracted. Second, these goal-oriented attentional self-regulation skills are practiced in daily life and actively applied to self-generated complex goals. Participants are asked to identify personally-relevant and feasible functional goals as individual and group projects. They are then trained in applying the goal management strategies on the functional task(s) of their choice. The main objective is to allow extensive practice and application of skills, thereby linking the attentional regulation directly to goal attainment efforts.

The EDU training is an active comparison matched with GOALS for therapist time, for homework load, and participation in a group. It involves ten 2 hour sessions of group-based training, three individual 1 hour training sessions, and approximately 20 hours of home practice. It is conducted in a small group format with 2-5 participants and 2 therapists per group. The EDU training is designed to be engaging and provide information about brain functioning and brain health.

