### **Assessments**

At baseline (pre GOALS or EDU), week 5, week 10 (post GOALS for those who began with EDU), and at 6 months, participants will be evaluated with a multi-level battery of measures assessing:

1. Neuro-cognitive performance focusing on neuropsychological measures of complex attention, executive function and memory.
2. Functional performance on complex 'real-life' tasks involving multitasking and goal management
3. Emotional regulation and daily functioning.

*Neuropsychological Assessment:* The neuropsychological battery used in this study was developed to assess performance in cognitive domains of *complex attention and executive function* that are commonly affected by both TBI and PTSD and targeted by GOALS training. *Working Memory* will be assessed with (1) Letter Number Sequencing, WAIS IV and (2) Auditory Consonant Trigrams. *Sustained attention* will be assessed with the timed Digit Vigilance test. *Inhibition of Automatic Responding* will be assessed with DKEFS Stroop Inhibition (time and error score). *Mental Flexibility* will be assessed with: (1) Trails B and (2) DKEFS Stroop Inhibition-Switching. Performance on *verbal memory* tests will be assessed with Hopkins Verbal Learning Test - HVLT-R.

Participants' performance in cognitive domains commonly affected by TBI and PTSD, but not targeted by the intervention, will also be assessed as a marker of potential non-specific changes. *Processing speed* will be assessed with (1) Trails A, requiring rapidly connecting in order numbers on a page, and with (2) DKEFS Stroop Color Naming and (3) DKEFS Stroop Word Reading. Intellectual functions estimate will be assessed at baseline with Wechsler Test of Adult Reading- WTAR. The purpose of the WTAR is to estimate pre-morbid intellectual ability. The overall battery of neurocognitive tests will take approximately 1 hour.

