### ***Follow-up***

At 6 months post-baseline, participants will be re-evaluated with the above-described multi-level battery of measures.

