3.0 Objectives

- Describe the study's purpose, specific aims, or objectives.
- State the hypotheses to be tested.

The overall aim of this proposal is to investigate potential short- and long-term effects of a cognitive training program that targets executive control functions of attentional self- regulation

and goal management, Goal-Oriented Attentional Self-regulation (GOALS), in Veterans with comorbid PTSD - mTBI and cognitive difficulties.

Aim 1: Determination of short and long term effects of cognitive training on neuro-cognitive performance:

Hypothesis 1: Participants who perform GOALS training will demonstrate greater improvements on untrained standardized neuropsychological measures of complex attention and executive function compared to participants who participate in control EDU training.

Hypothesis 2: Improvements in complex attention and executive function will be sustained at six months post GOALS training, suggesting persistence of training benefits.

Aim 2: Determination of short and long term effects of cognitive training on complex real-life functional task performance and daily functioning:

Hypothesis 1: Participants who perform GOALS training will demonstrate greater improvements on untrained complex real-life functional task performance compared to participants who participate in control EDU training.

Hypothesis 2: Participants who perform GOALS training will report greater improvements on self-report measures of daily functioning compared to participants who participate in control EDU training.

Hypothesis 3: Improvements in complex functional task performance and on self-report measures of daily functioning will be sustained at six months post GOALS training, suggesting persistence of training benefits.

Aim 3: Determination of short and long term effects of cognitive training on emotional regulation:

Hypothesis 1: Participants who perform GOALS training will report greater improvements on self-report measures of emotional regulation compared to participants who participate in control EDU training.

Hypothesis 2: Improvements on self-report measures of emotional regulation measures will be sustained at six months post GOALS training, suggesting persistence of training benefits.

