5.0 Study Procedures

5.1 Study Design

 Describe experimental design of the study. Include sequential and/or parallel phases of the study, including durations, and explain which interventions are standard of care.

The proposed study includes two interventions, as well as pre- and post-intervention assessments.

Participants who meet the inclusion criteria will be enrolled in the study and randomized to either a five-week comparison intervention (Brain Health Education - EDU) or an experimental intervention (Goal-Oriented Attentional Self-regulation training – GOALS).

After 5 weeks, those who enter with EDU will receive 5 weeks of GOALS, while those who begin with GOALS will have no further formal training.

Both groups will participate in assessments at baseline, week 5 and week 10. Long-term followup will be conducted at 6 months.

Time Commitment: Assessment: Neurocognitive assessments and self-report forms take up to 3 hours and functional assessments take up to 2 hours to complete, or up to 4 hours combined. Assessments may be completed in one or two sessions. Participants are free to take breaks during testing sessions. Participants participate in assessments four times during the course of the study (baseline, at 5 weeks, at 10 weeks, and at 6 months), or up to 20 hours (5 hours x 4 time points).

Participants will be randomly assigned to one or two 10-session interventions (GOALS and EDU), each lasting about 5 weeks. Intervention sessions last about 2 hours, with 2 group sessions per week and 3 one-hour individual sessions over the period of training. Participation in GOALS alone requires about 63 hours total (20 hours group sessions, 3 hours individual sessions, 20 hours homework, and up to 20 hours assessments). Participation in both GOALS and EDU requires about 106 hours total (40 hours group sessions, 6 hours individual sessions, 40 hours homework, and 20 hours assessments).

The interventions do not involve standard of care.

• Include a description of how anticipated risk will be minimized and include an analysis of risk vs. potential benefit.

Potential risks are minimal. The research procedures involved in this study present no physical risk and minimal psychological risk to the subjects. The primary risk in this study is the potential for anxiety (including possibility of exacerbation of PTSD

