5.6 Data Analysis

• Provide sample size determination and analysis (include anticipated rate of screen failures, study discontinuations, lost to follow-up etc.).

We estimated sample size requirements for the primary hypotheses for each aim based on the actual preliminary data from veterans who underwent GOALS training. For Attention and Executive Function Overall Domain z score (AVEXE) we found a standardized effect size of 1.2, for the GPS Overall Domain Score (GPSTA) and the Mayo Portland Adaptability Inventory Total Score (MPTST) we found a standardized effect size of 1.1, and for the POMS Total Mood Disturbance Score (POMSTMDZ) we found a standardized effect size of 0.8. Therefore, using the lowest effect size we would estimate that a feasible sample size of 42 patients (21 per group) for each intervention (GOALS and EDU) should yield a power of .80 at an alpha level of 0.05 to detect a standardized effect size of 0.8 or larger.

• Describe how, where and by whom the data will be analyzed.

Tests of repeated measures will be used to assess the effects of the training interventions on pre- and post- intervention measurements. Intervention group x time interactions will be assessed using ANOVA and specific relationships will be tested using paired T-tests.

Practice Effects: Because of repeated testing, improvements on some assessments may be partially due to practice. As a sensitivity analysis, we will compare tests using absolute change scores (as described above) to those using a change index that corrects for practice effects [70]. Specifically, change is operationalized as ((X2-X1)-(M2-M1))/SED, where X1, M1, and X2, M2 are the baseline and follow-up scores for a participant and corresponding group means, respectively; SED is the standard error of the difference. These results will be compared to those obtained from the regression models.

The PI and co-investigators will perform data analysis.

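### Both arms have received GOALS by 6 months, so improvement from baseline at that visit is an uncontrolled within-person change and cannot by itself show that GOALS benefits persist

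*Protocol*

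**What the plan says.** Participants are randomised to five weeks of GOALS or of EDU. After that, "those who enter with EDU will receive 5 weeks of GOALS, while those who begin with GOALS will have no further formal training" (Protocol, Interventions; the same design is in the Combined protocol and SAP, 5.1). Both arms are tested at baseline, week 5, week 10 and 6 months.

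The long-term hypotheses are worded in several ways:

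- Protocol, Question 1, Hypothesis 2: average improvement at 6 months "relative to their baseline performance, suggesting persistence of GOALS training benefits".
- Protocol, Question 2, Hypothesis 3 and Question 3, Hypothesis 2: improvement relative to performance before GOALS.
- Combined protocol and SAP, 3.0: "Improvements in complex attention and executive function will be sustained at six months post GOALS training, suggesting persistence of training benefits", with parallel wording for Aims 2 and 3 and no stated reference value. Its Abstract refers to baseline functioning for all three domains.

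None names a comparator, margin or threshold.

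On rival explanations, section 5.6 accepts that "improvements on some assessments may be partially due to practice". It plans, as a sensitivity analysis, a change index that subtracts a mean change M2-M1. The Protocol's Assessments section adds processing-speed tests, outside the training target, which "will also be assessed as a marker of potential non-specific changes".

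**The concern.** The plan reads a 6-month gain as evidence about GOALS, but at that visit nobody is free of GOALS. A group-by-time test at 6 months compares GOALS first with EDU then GOALS, which says nothing about GOALS against no GOALS. What remains is before-and-after change in people tested for the fourth time ("Participants participate in assessments four times during the course of the study") who were enrolled because they had current difficulties. Retest gain and regression to the mean push such change upward whether or not the training lasts.

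At stake is the long-term half of each aim. A benefit present at week 5 and gone by 6 months could still be reported as lasting.

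**Working it through.** **What the plan's own figure covers.** Section 5.6 states power 0.80 for 21 per group, standardized effect 0.8, alpha 0.05. With noncentrality 0.8 × √(21/2) = 2.59 and 40 df, power is 0.817 one-sided and 0.716 two-sided. The figure reproduces if the test is one-sided; sidedness is not stated. It concerns GOALS against EDU and gives no error rate for the 6-month conclusion.

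**Which comparisons are GOALS-free.**

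| Interval | GOALS-first | EDU-first | GOALS-free comparator |
|---|---|---|---|
| Baseline to week 5 | GOALS | EDU | Yes, randomised |
| Week 5 to week 10 | No formal training | GOALS | No |
| Baseline to 6 months | GOALS received | EDU and GOALS received | No |

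For EDU-first participants, the Question 1 reference value precedes EDU, so any EDU effect also counts towards the 6-month gain. For Questions 2 and 3, performance before GOALS is most naturally their week-5 value, which already contains one retest and five weeks of EDU.

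**How often a non-specific gain alone would look like improvement.** Inputs from the documents: 42 completers, 21 per arm, paired t-tests, alpha 0.05. Assumed, because the documents are silent: no GOALS effect at 6 months, two-sided testing, non-specific gain g in baseline SDs, equal SDs at both visits, test-retest correlation r.

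- SD of change = √(2(1 − r)); at r = 0.7 this is √0.6 = 0.775.
- Noncentrality = g/0.775 × √n. For g = 0.3: 0.387 × √42 = 2.51 with 42, and 0.387 × √21 = 1.77 with 21.
- Critical t: 2.020 (41 df) and 2.086 (20 df).

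Probability of significant improvement at r = 0.7, with the range over r = 0.5 to 0.8 in brackets:

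| Gain | 42 pooled | 21 (one arm) |
|---|---|---|
| 0 | 2.5% | 2.5% |
| 0.1 SD | 13% (9–17%) | 8% (6–10%) |
| 0.2 SD | 37% (24–52%) | 20% (14–28%) |
| 0.3 SD | 69% (48–85%) | 39% (26–54%) |
| 0.4 SD | 90% (72–98%) | 61% (41–79%) |

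**Whether the practice index helps.** The index is ((X2 − X1) − (M2 − M1))/SED, with M1 and M2 called the corresponding group means. If these are the participant's own group, the mean of X2 − X1 over that group equals M2 − M1, so the index averages zero whatever the effect. If they are the other arm's 6-month means, that arm has also had GOALS. The only GOALS-free retest estimate in the trial is the EDU arm's baseline-to-week-5 change: one retest, and it includes any EDU effect.

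**Precision of a contrast with that estimate.** At r = 0.7, with the same SD of change in both terms, the standard error of (GOALS-first change to 6 months) minus (EDU change to week 5) is 0.775 × √(2/21) = 0.239. The single-arm paired test has 0.775/√21 = 0.169 (ratio 1.4), and the pooled test 0.775/√42 = 0.120 (ratio 2.0). Two-sided significance needs about 2.021 × 0.239 = 0.48 SD.

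**The case against.** The strongest reply is that the plan is more careful than the structural point suggests. It provides a practice-corrected sensitivity analysis, an untargeted marker domain and alternate forms of the Goal Processing Scale. It also requires the chronic stable phase and stable medication, and advises participants to keep the same therapy for the study's duration. The hypotheses are hedged as suggesting persistence, and sustained improvement presupposes an improvement at week 5, where an ineffective training should fail the randomised comparison.

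Much of this stands as mitigation. Stability criteria make natural course the weakest rival. Test practice is a less obvious route for the self-report measures of Aims 2 and 3. None of it supplies a control at 6 months: the index has no GOALS-free mean change, no rule links the marker domain to the conclusion, and the scale has three forms for four sessions and is not a Question 1 measure.

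A reader might infer more than the documents support:

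- That retest gain alone would satisfy the hypothesis. This follows only for the bare on-average wording with some positive expected gain, and then only in expectation. Under a significance test it is a probability that depends on assumed inputs, as low as 6% to 17% for a 0.1 SD gain.
- That all aims are equally exposed. In the Protocol's hypotheses only Question 1 uses pre-intervention baseline.
- That the finding of efficacy is undermined. The week-5 contrast is randomised and does not depend on this.

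**Conclusion.** The point holds as a limit on interpretation. That no GOALS-free comparator exists at 6 months follows from the design and needs no assumption. The plan therefore cannot attribute 6-month improvement to GOALS from within-person change alone, most clearly in Question 1, Hypothesis 2. The practical exposure is mainly a short-lived benefit read as a lasting one. How often that would happen depends on a gain and a correlation the documents do not give. Across the values examined, the risk runs from modest to very high and is greatest when the arms are pooled. The trial and its crossover design stand; the inference drawn from the 6-month visit should change.

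**What to change.** 1. In section 5.6 and in the long-term hypotheses, describe the 6-month result as an uncontrolled within-person change in people who received GOALS. Remove the statement that improvement from baseline suggests persistence of GOALS benefits. State one reference value per hypothesis.
2. Define M2-M1 in the practice index as the EDU arm's baseline-to-week-5 change, and call it a minimum allowance.
3. Report two contrasts beside the 6-month change, as supporting and not gating evidence:
   - (a) The GOALS-first baseline-to-6-month change minus the EDU baseline-to-week-5 change, with a confidence interval. It sets a third retest at 6 months against a first retest at 5 weeks, so further practice can still inflate it.
   - (b) For cognition, the attention and executive change beside the processing-speed change, noting that practice gains may differ by domain.
4. Reconcile the timing. Section 3.0 speaks of six months after GOALS, while the Protocol's Follow-up section says "At 6 months post-baseline, participants will be re-evaluated with the above-described multi-level battery of measures". Taking 6 months as 26 weeks, that is about 21 weeks after GOALS in one arm (26 − 5) and 16 in the other (26 − 10).

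The cost is wording and two contrasts on data already collected. The long-term claim becomes more modest, and contrast (a) is less precise than either paired test. The Protocol's Progress to date section says follow-up had ended and analysis had begun, so the added contrasts should be labelled post hoc.

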## **Methods**

### ***Eligibility criteria***

Inclusion criteria: Veterans, ages 18 to 75 years, with at least 12 years of education, a current diagnosis of PTSD (DSM IV-R), and a history of mild traumatic brain injury, defined by the American Congress of Rehabilitation Medicine (ACRM) and VA, as a traumatically-induced physiological disruption of brain function.

Exclusion Criteria: History of moderate or severe TBI (defined by ACRM as having an injury that includes a loss of consciousness lasting longer than 30 minutes, or post-traumatic amnesia lasting longer than 24 hours). Unstable medical, neurologic, or psychiatric condition, including severe cognitive dysfunction, or other reasons for being unable or unwilling to participate in the training and assessments; ongoing illicit drug or alcohol abuse (AUDIT>8); psychosis, severe depression, anxiety or PTSD precluding participation in research activities; current evidence-based PTSD remediation therapy; and, poor English comprehension.

### ***Interventions***

Participants who meet the inclusion criteria will be enrolled in the study and randomized to either five week Brain Health Education (EDU) or Goal-Oriented Attentional Self-regulation (GOALS) training. After 5 weeks, those who enter with EDU will receive 5 weeks of GOALS, while those who begin with GOALS will have no further formal training. Both groups will participate in assessments at baseline, week 5 and week 10. Long-term follow-up will be conducted at 6 months.

The GOALS training involves ten 2 hour sessions of group-based training, three individual 1 hour training sessions, and approximately 20 hours of home practice. It is conducted in a small group format with 2-5 participants, and 2 therapists per group.

The GOALS intervention emphasizes two key components: First, regulation of distractibility (redirection of attention to goal-relevant processes and the filtering of non-relevant 'noise', especially in the context of distractions) is addressed with attention regulation training. Training emphasizes principles of applied mindfulness-based attention regulation to redirect cognitive processes towards goal-relevant activities even when distracted. Second, these goal-oriented attentional self-regulation skills are practiced in daily life and actively applied to self-generated complex goals. Participants are asked to identify personally-relevant and feasible functional goals as individual and group projects. They are then trained in applying the goal management strategies on the functional task(s) of their choice. The main objective is to allow extensive practice and application of skills, thereby linking the attentional regulation directly to goal attainment efforts.

The EDU training is an active comparison matched with GOALS for therapist time, for homework load, and participation in a group. It involves ten 2 hour sessions of group-based training, three individual 1 hour training sessions, and approximately 20 hours of home practice. It is conducted in a small group format with 2-5 participants and 2 therapists per group. The EDU training is designed to be engaging and provide information about brain functioning and brain health.

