This research is designed to contribute to improving care by (1) providing a neuroscientific framework for understanding neurorehabilitation therapies and their effects on executive control functions and emotional regulation; and (2) aiding in the design of novel therapeutic interventions that more directly target the underlying cognitive bases of dysfunction. Completion of the proposed studies will provide an essential foundation for the immediate next steps -- directly targeting the elucidated neural pathways using improved behavioral, physiological (e.g. transcranial magnetic stimulation) and pharmacologic modulation treatment interventions.

 Provide description of the study population (delineate all categories of subjects – patients, providers, family members, employees, etc.). Include anticipated enrollment numbers

Total planned enrollment is 54. Subjects will be Veterans, ages 18 to 55 years, with at least 12 years of education, a current diagnosis of PTSD (DSM IV-R), and a history of mild traumatic brain injury.

- As applicable, provide information on any added protections for vulnerable populations. N/A
- If applicable include information on data and specimen banking. N/A

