5.2 Recruitment Methods

• State how many subjects will be needed.

About 80 subjects will be recruited and enrolled to meet the enrollment target of 54, out of which it is anticipated 42 will complete the study.

• Describe when, where, how and by whom potential subjects will be identified and recruited.

Recruitment material includes a brochure, flier, and letters to potential participants, clinicians, and service providers. Participants will not be cold called. Researchers will call potential participants only if returning a call or a request to call (e.g., if potential participant left a note requesting phone contact). Recruitment activities will include presentations to individuals and groups associated with PTSD, as well as distribution of approved letters, brochures and flyers. Recruitment activities will target VA clinicians, VA Outpatient Clinics, Veteran Centers, State of California Department of Rehabilitation Veteran Services Programs, Employment Development Department Veterans Outreach programs, County Veterans Services, college programs for veterans, and Travis AFB Transition Service Center, as well as mental health and neurology clinics in local hospitals. Brochures and fliers will be placed in locations approved by the facility being visited, e.g., bulletin boards and brochure display tables. Clinicians on the research team may also provide an-IRB approved brochure or letter to selected patients who may be interested

Step-by-Step Recruitment Process: Research team members will contact or visit the above entities and request permission to leave off brochures, flyers and letters and will also ask if any clinicians or other service staff might be interested in hearing more about the research. If so, researchers will schedule a presentation to clinicians or service providers. Clinicians or service providers may invite potential subjects to these presentations. Brochures, flyers and letters will be available for distribution at presentations. If clinicians or service providers contact the researchers to refer a potential subject, they will be asked to have the subject initiate contact with the research team. If a potential subject expresses interest in person (e.g., at a presentation or if simply observing brochures being distributed), a telephone appointment will be scheduled to discuss the possibility of participation.

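### Both trainings run in small groups, but the planned ANOVA and sample size treat participants as independent; if change is correlated within groups, the week-5 GOALS-minus-EDU standard error is too small.

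*Protocol*

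**What the plan says.** The Protocol (Interventions) describes GOALS delivery in these words: "It is conducted in a small group format with 2-5 participants, and 2 therapists per group". It gives EDU the same group size and number of therapists. Each training has ten 2-hour group sessions and three 1-hour individual sessions. Section 5.1 of the combined protocol and SAP gives the load of GOALS alone as "20 hours group sessions, 3 hours individual sessions, 20 hours homework". Part of the GOALS content is itself a group activity: "Participants are asked to identify personally-relevant and feasible functional goals as individual and group projects".

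The analysis text is section 5.6. It states: "Intervention group x time interactions will be assessed using ANOVA". There, intervention group means the randomized arm. Paired t-tests follow, then a practice-effect sensitivity analysis that ends: "These results will be compared to those obtained from the regression models". Those regression models are not described. The sample size sentence reads: "42 patients (21 per group) for each intervention (GOALS and EDU) should yield a power of .80". It mentions neither an ICC nor a design effect. No term for training group, cohort or therapist appears elsewhere in the documents.

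On numbers, section 5.1 says "Total planned enrollment is 54", and section 5.2 adds "out of which it is anticipated 42 will complete the study". The Protocol (Progress to date) reports 76 enrolled, enrollment closed and data analysis begun.

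**The concern.** Participants are randomized one by one but trained together. Members of a training group share two therapists, the same sessions, the same peers and some joint projects. Group sessions are 20 of 23 contact hours (87%), or 20 of 43 hours (47%) if home practice is counted. Their changes from baseline to week 5 may therefore be more alike than those of people in different groups. Individual randomization does not prevent correlation that arises during treatment.

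The week-5 contrast matters most here. It is the only between-arm comparison made before the EDU arm receives GOALS, and it carries the between-arm hypotheses of all three aims. If change is positively correlated within training groups, the planned test reports too narrow an interval and too small a p-value, and a borderline result could be called significant when it should not be.

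**Working it through.** **Inputs.** From the documents: 21 analysed per arm, effect 0.8, alpha 0.05 (section 5.6); groups of 2 to 5 in both arms (Protocol, Interventions). Assumed, because the documents do not say: ICC of change 0 to 0.20; stable group membership; a two-sided test; two visits (baseline and week 5), so that arm by time equals a pooled two-sample t-test on change with 40 degrees of freedom. Section 5.6 does not say which of the four assessments enter the ANOVA.

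**The plan's own figure.** With independent participants, 21 per arm and an effect of 0.8, a t-test has power 0.817 one-sided and 0.716 two-sided. The stated .80 is thus met only one-sided. Section 5.6 gives no sidedness. That is a separate matter and is not caused by clustering. The figure contains no design effect.

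**How many groups.** With 54 enrolled and equal arms, 27 per arm start: 27/5 = 5.4, so at least 6 groups, and at most 13 with a minimum of 2 in each. From 21 completers the range is 5 to 10. These counts are illustrative, because 76 were enrolled and the number who started training is not stated.

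**Standard error, 7 groups of 3 per arm.** Set the total variance of change to 1 and the group variance to the ICC.

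- True variance of the arm difference: (2/21)(1 + 2 ICC).
- Expected pooled variance: [12(1 + 2 ICC) + 28(1 − ICC)]/40 = 1 − ICC/10.
- True SE over reported SE: √[(1 + 2 ICC)/(1 − ICC/10)].
- At ICC 0.10: √(1.20/0.99) = 1.10.

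**Type I error.** The pooled variance times 40 is distributed as (1 + 2 ICC)χ²(12) + (1 − ICC)χ²(28). Averaging the normal tail probability over that distribution gives the error of the planned test. The last column is simulated, for nine groups of 2 and one of 3, and for four groups of 4 and one of 5.

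| ICC | True SE | True/reported SE | Error, groups of 3 | Error, groups of 2 to groups of 4-5 |
|---|---|---|---|---|
| 0 | 0.309 | 1.00 | 5.0% | 5.0% |
| 0.01 | 0.312 | 1.01 | 5.2% | 5.1-5.4% |
| 0.05 | 0.324 | 1.05 | 6.2% | 5.7-6.9% |
| 0.10 | 0.338 | 1.10 | 7.4% | 6.3-9.0% |
| 0.20 | 0.365 | 1.20 | 9.9% | 7.8-13.0% |

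If only GOALS groups are correlated, the groups-of-3 column reads 5.0, 5.1, 5.6, 6.2 and 7.4%.

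**Can the trial's own data settle the ICC?** No. With 14 groups of 3 and a true ICC of 0.05, 95% of ANOVA estimates lie between −0.26 and 0.38, and 41% are zero or negative.

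**Which cluster analysis.** A test with training group as the unit of error has 14 − 2 = 12 degrees of freedom and holds 5.0% at any ICC under these assumptions. Its power at an effect of 0.8, from the noncentral t, is 0.66 at ICC 0 and 0.62 at ICC 0.05. The planned test has 0.72 and 0.71, the second with its inflated error. A version that falls back to the participant-level test whenever the group variance estimate is zero or negative has error of 3.6% to 4.3% over ICC 0 to 0.10, and power 0.64 and 0.61. It is conservative and loses more power.

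**The case against.** The strongest reply is that the harm rests on a number the documents do not contain. At ICC 0.01 the error is at most about 5.4%, which would change no conclusion. Some features of the plan also point away from strong clustering: goals are personal as well as shared, part of the training is individual, and the same staff work at both sites, which limits staff differences between sites. All of this stands. None of it rules out correlation specific to one training group, but it keeps the point conditional.

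Second, a cluster analysis is not free. It loses power, and the version that drops the group term when its variance estimate is not positive is as far below 5% at ICC 0.05 as the planned test is above it (4.0% against 6.2%). This stands too, and it is why the fix names one version. Adding several models per measure after analysis has begun, with no rule for reading them, would create a new problem.

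Third, enrollment is closed, so a design effect can no longer change the sample size. That is correct. What remains is disclosure and a sensitivity analysis.

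A reader might infer more: that error is really near 13%, that clustering explains why two-sided power is 0.72 and not .80, or that the preliminary week-5 improvement in Progress to date is false. The documents support none of these. The 13% needs an ICC of 0.20 together with groups of 4-5. The power gap is present at ICC 0. The preliminary results come without estimates, standard errors or group composition.

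**Conclusion.** The point holds as a conditional risk. Both arms are trained in groups, and the stated analysis and sample size allow for none of that. With any positive ICC of change the standard error is too small. The understatement is negligible near ICC 0.01, about 5% to 10% of the standard error at ICC 0.05 to 0.10 with groups of 3 (error about 6% to 7%), and larger only with bigger groups or a higher ICC. These sizes rest on an assumed ICC, stable membership, two visits, 21 analysed per arm and clustering in both arms. The remedy is inexpensive and worth having, but nothing here shows that the planned result is wrong.

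**What to change.** 1. Keep the planned ANOVA as the main result.
2. For each main measure, add one sensitivity analysis of the baseline-to-week-5 arm contrast. Date it and label it as added after data analysis started. Use training group, nested in arm and acting on change, as the unit of error, with between-group degrees of freedom. Keep the group term even when its variance estimate is zero or negative. A group intercept that is constant over time is not enough: it cancels in the change and leaves the arm-by-time standard error as it was.
3. State the reading rule before running it: if the planned result is significant and the cluster-level interval includes zero, describe the result as sensitive to within-group correlation.
4. In section 5.6, say that the power figure assumes independent participants and specify the regression models.
5. Report the number and size of training groups per arm, how they were formed, and any change in membership.

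A table of the contrast at fixed ICCs (0, 0.01, 0.05, 0.10, 0.20) is optional.

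Cost: no new data, provided delivery records show who trained with whom (assumed). Intervals will be wider. With 7 groups of 3 per arm, two-sided power at an effect of 0.8 is 0.66 instead of 0.72 if the ICC is 0, and 0.62 instead of 0.71 if it is 0.05. A cluster-level interval that includes zero may therefore reflect lost precision alone, which is why the rule says sensitive and not refuted.
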